# 14.3.6.2 Estimand strategy for binary endpoints

The population level summary will be the difference in response rates between delgocitinib cream 20 mg/g and cream vehicle.

## Primary estimand: 'composite' strategy

This primary estimand evaluates the treatment effect in adult subjects with moderate to severe CHE, without initiation of rescue treatment or permanent discontinuation of IMP.

For subjects who received rescue treatment or who have permanently discontinued IMP prior to the endpoint of interest, observed data after the IEs will be considered non-response, reflecting an assumption that initiation of rescue treatment and permanent discontinuation of IMP indicate failure of the randomised treatment.

For example, the primary composite endpoint of IGA-CHE TS at Week 16 without initiation of rescue treatment or permanent discontinuation of IMP can take the values:

- '1' (response), if the subject achieves IGA-CHE TS at Week 16 and has not initiated rescue treatment nor permanently discontinued IMP prior to Week 16.
- '0' (non-response), if the subject has not achieved IGA-CHE TS at Week 16 or has initiated rescue treatment or permanently discontinued IMP prior to Week 16.

### Primary analysis for the primary estimand

Missing data for subjects who do not attend the visit for the endpoint of interest and do not experience an IE prior to this visit will be imputed as non-response.

The difference in response rates between the two treatment groups will be analysed using the CMH test stratified by region and baseline IGA-CHE score. The difference in response rates with 95% CI will be calculated by the Mantel-Haenszel method stratified by region and baseline IGA-CHE score.

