## 14 Statistical methods

## 14.1 Sample size

A total of 450 subjects will be randomised 2:1 to delgocitinib cream 20 mg/g or cream vehicle. The sample size is chosen to ensure that sufficient safety information including adequate long-term exposure data is collected.

With a one-sided significance level of 2.5%, a sample size of 450 subjects randomised will provide at least 99% power for detecting a treatment difference for the primary endpoint, assuming an IGA-CHE TS response rate at Week 16 of 40% vs. 10% for delgocitinib cream 20 mg/g and cream vehicle, respectively. The assumptions on response rates are based on results from the phase 2b dose-ranging trial (LP0133-1273).

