### Primary analysis for the primary estimand

Missing data for subjects who do not attend the visit for the endpoint of interest and do not experience an IE prior to this visit will be imputed as WOCF (including the baseline value).

The change (or percentage change) from baseline to the endpoint of interest will be analysed using an ANCOVA model with effects of treatment group, region, baseline IGA-CHE score, and baseline value (endpoint of interest).

Page 114 of 157

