Reduction of HESD itch score (weekly average) of ≥4 points from baseline at Week 8¹  Reduction of HESD itch score (weekly average) of ≥4 points from baseline at Week 4¹  Reduction of HESD itch score (weekly average) of ≥4 points from baseline at Week 2¹  Reduction of HESD score (weekly average) of ≥4 points from baseline at Week 8²  Reduction of HESD score (weekly average) of ≥4 points from baseline at Week 8²  Reduction of HESD score (weekly average) of ≥4 points from baseline at Week 4²	Binary	Composite	Non-response imputation	Pandemic modified composite	Independent of the COVID-19 pandemic: non-response imputation  Related to the COVID-19 pandemic: MI assuming MAR within treatment group	Not applicable	Not applicable

Page 120 of 157

		Primar	y estimand	First supp	First supplementary estimand		lementary estimand
Key secondary endpoint	Type of endpoint	Strategy to handle IEs	Handling of missing data and data collected after IE	Strategy to handle IEs	Handling of missing data and data collected after IE	Strategy to handle IEs	Handling of missing data and data collected after IE
Reduction of HESD pain score (weekly average) of ≥4 points from baseline at Week 16 	Binary	Composite	Non-response imputation	Pandemic modified composite	Independent of the COVID-19 pandemic: non-response imputation  Related to the COVID-19 pandemic: MI assuming MAR within treatment group	Treatment policy	Independent of the COVID-19 pandemic: MI assuming MAR within treatment group and occurrence of IEs  Related to the COVID-19 pandemic: MI assuming MAR within treatment group
Reduction of HESD pain score (weekly average) of ≥4 points from baseline at Week 8³ Reduction of HESD pain score (weekly average) of ≥4 points from baseline at Week 4³	Binary	Composite	Non-response imputation	Pandemic modified composite	Independent of the COVID-19 pandemic: non-response imputation  Related to the COVID-19 pandemic: MI assuming MAR within treatment group	Not applicable	Not applicable

 Trial ID: LP0133-1402
 Date: 20-Aug-2021
 Version: 4.0, Final

 Page 121 of 157

		Primary estimand		First supplementary estimand		Second supp	lementary estimand
Key secondary endpoint	Type of endpoint	Strategy to handle IEs	Handling of missing data and data collected after IE	Strategy to handle IEs	Handling of missing data and data collected after IE	Strategy to handle IEs	Handling of missing data and data collected after IE

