Reduction of DLQI score of ≥4 points from baseline at Week 16 	Binary	Composite	Non-response imputation	Pandemic modified composite	Independent of the COVID-19 pandemic: non-response imputation  Related to the COVID-19 pandemic: MI assuming MAR within treatment group	Treatment policy	Independent of the COVID-19 pandemic: MI assuming MAR within treatment group and occurrence of IEs  Related to the COVID-19 pandemic: MI assuming MAR within treatment group

- 1) Among subjects with a baseline HESD itch score (weekly average) ≥4 points.
- 2) Among subjects with a baseline HESD score (weekly average) of ≥4 points.
- 3) Among subjects with a baseline HESD pain score (weekly average) of  $\geq 4$  points.
- 4) Among subjects with a baseline DLQI score of ≥4 points.

Abbreviations: COVID-19 = coronavirus disease 2019; DLQI = Dermatology Life Quality Index; HECSI = Hand Eczema Severity Index; HECSI-75 = at least 75% improvement in HECSI from baseline; HECSI-90 = at least 90% improvement in HECSI from baseline; HESD = Hand Eczema Symptom Diary; HEIS = Hand Eczema Impact Scale; IE = intercurrent event; IGA-CHE = Investigator's Global Assessment for chronic hand eczema; IGA-CHE TS = IGA-CHE treatment success, i.e. an IGA-CHE score of 0 (clear) or 1 (almost clear) with a ≥2 step improvement from baseline; IMP = investigational medicinal product; MAR = missing at random; MI = multiple imputation; PDAL = Proximal Daily Activity Limitations; WOCF = worst observation carried forward.

Page 124 of 157

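### Eleven key secondary responder endpoints (reduction of ≥4 points) are tested without the scale's own baseline score: valid, but a modest amount of precision is given up

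*Combined protocol and SAP*

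**What the plan says.** Section 14.3.6.2 (binary endpoints, primary analysis for the primary estimand) has the difference in response rates "analysed using the CMH test stratified by region and baseline IGA-CHE score". The estimate and its 95% CI come from the Mantel-Haenszel method with the same strata. The sensitivity and supplementary analyses of binary endpoints in that section also end in a CMH analysis with these strata.

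Section 14.3.6.3 (continuous endpoints) specifies an ANCOVA with treatment group and "region, baseline IGA-CHE score, and baseline value (endpoint of interest").

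Panel 24 in Section 14.3.8 lists both versions of four scales. The responder versions include "Reduction of HESD itch score (weekly average) of ≥4 points from baseline at Week" 16 (and Weeks 8, 4 and 2) and "Reduction of DLQI score of ≥4 points from baseline at Week 16". The continuous versions are change to Week 16 in HESD itch, HESD, HESD pain and DLQI. For the responder endpoints, baseline enters only as a restriction to subjects with a baseline score of at least 4. No reason is given for treating the two versions differently.

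Section 14.1 states power for the primary endpoint only.

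**The concern.** The responder rule is an absolute drop of 4 points on scales with a floor at 0 (HESD items run 0–10, DLQI 0–30). A subject who enters at 4 must reach 0 to respond, while one who enters at 9 need only reach 5. The baseline score therefore limits who can respond. It is known for everyone in these analysis subsets, because membership depends on it. Baseline IGA-CHE is not a substitute: it has two levels here, is rated by the investigator, and contains no itch, pain or quality-of-life item.

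At stake is precision on 11 confirmatory tests. They sit in a procedure with alpha splitting, so some may run below one-sided 2.5%. No power is stated for any of them, and the HESD, pain and DLQI subsets may be smaller than 450.

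**Working it through.** **Inputs from the documents.** "A total of 450 subjects will be randomised 2:1", that is 300 vs 150; one-sided alpha 2.5%; primary endpoint assumed at 40% vs 10% (Section 14.1). The vehicle rate for the itch responder rule at Week 16 was about 20% in the phase 2b trial (Section 14.3.6.2, first sensitivity analysis).

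**Inputs that are assumptions.** The documents give no baseline distributions, no delgocitinib rates for these endpoints and no local alphas (the Panel 22 graphic is not available here). Those values below are assumed.

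**1. The plan's own figure.** SE = √(0.40×0.60/300 + 0.10×0.90/150) = √0.0014 = 0.0374. Then 0.30/0.0374 = 8.02, and Φ(8.02 − 1.96) exceeds 99.99%. This agrees with "at least 99% power for detecting a treatment difference for the primary endpoint". It says nothing about the 11 endpoints.

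**2. Count.** Itch 4 + HESD 3 + pain 3 + DLQI 1 = 11.

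**3. Variance reduction, simulated.** The trials used stratified 2:1 allocation and counted intercurrent events as non-response (8% vs 18% assumed). The planned Mantel-Haenszel risk difference was compared with a logistic regression that adds the continuous baseline score, standardised to a risk difference.

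| Scenario (assumed) | SD planned | SD adjusted | Reduction, 1 − (ratio)² |
|---|---|---|---|
| Itch, proportional model | 0.0406 | 0.0399 | 3.4% |
| Itch, regression model | 0.0425 | 0.0420 | 2.3% |
| DLQI, 38% vs 58% | 0.0496 | 0.0485 | 4.4% |

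A second set of simulations gave 3.7% and 7.6% (itch, two noise levels), 6.3% (pain, n = 300) and 5.8% (DLQI, n = 420). The mean risk difference was unchanged (for example 0.1473 with both methods), so the target quantity stays the same. The working range is roughly 2–8%.

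**4. What that buys.** Power = Φ(difference/(SE×√(1 − v)) − z), where v is the variance reduction.

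Itch 20% vs 33% (the 33% is assumed): SE = √(0.33×0.67/300 + 0.20×0.80/150) = 0.0425, and 0.13/0.0425 = 3.06.

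| v | Power at 2.5% | Power at 0.5% (assumed split) |
|---|---|---|
| 0 | 86.5% | 68.6% |
| 2% | 87.1% | 69.7% |
| 8% | 89.1% | 73.1% |

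With the simulated SDs from step 3 at 2.5%:
- Itch difference 0.16: 97.6% to 98.0%, and 96.4% to 96.8%.
- Itch difference 0.13: 89.3% to 90.3%, and 86.4% to 87.2%.
- DLQI: 98.1% to 98.5%.

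Across most scenarios the gain is therefore about 0–2 points at 2.5%. The most favourable corner (8%, difference 0.13) gives 2.6. At 0.5% it is about 1–4 points.

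**5. Where the gain vanishes.** For itch 20% vs 40%, SE = 0.0432 and planned power is already 99.6%. With a weak baseline effect (log-odds of 0 to 0.2 per point), adding baseline gained nothing.

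**6. Validity of the plan.** In simulated null scenarios the planned CMH rejected in 2.2–2.4% of trials, against a nominal 2.5%.

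**7. Chance imbalance.** With an assumed baseline SD of 1.45, one SD of the between-arm difference is 1.45×√(1/300 + 1/150) = 0.145 points. At about 7 percentage points of response per baseline point (assumed), that shifts the estimate by about 1 percentage point, against an SE of about 4.

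**The case against.** The strongest defence is that nothing here is wrong. The CMH strata are the randomisation strata, and Section 12.1 names IGA-CHE severity as a strong prognostic factor. The test is valid for the stated summary, the difference in response rates. Each of the four scales also has a confirmatory Week 16 change endpoint adjusted for its own baseline, so adjusted evidence is already planned. A second analysis method for some binary endpoints adds complexity and needs a fallback. All of this stands, and it limits the point to an optional gain in efficiency.

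Three stronger readings are tempting, and the documents support none of them.

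- A reader might infer that chance imbalance in baseline biases the estimate. It does not: under randomisation that variability is already in the SE and the CI. Section 14.3.3 also has baseline values presented, so an imbalance would be visible.
- A reader might infer that baseline strongly drives response. The floor effect follows from the definitions, but its strength in this population is nowhere quantified, and the gradients used above are assumed.
- A reader might expect larger gains. Large-sample calculations under proportional improvement gave reductions of 5–13% for itch and 11–17% for DLQI. They ignored intercurrent events, which count as non-response and can weaken the link with baseline, so they are not a firm basis.

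The defence does not explain why the baseline value is used for the continuous versions of these scales and left out when the same scores are dichotomised.

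**Conclusion.** The point holds as a modest, avoidable loss of precision on 11 confirmatory endpoints. It is not an error: the planned CMH is valid and unbiased, type I error is controlled, and the primary endpoint is untouched. The likely size is a 2–8% lower variance of the risk difference, worth about 0–2 power points at one-sided 2.5% and somewhat more at a split alpha. These figures rest on assumed baseline distributions, delgocitinib rates, intercurrent-event rates and local alphas; only the 20% vehicle itch rate comes from the documents. Conclusions would rarely change. The gain matters most for moderate effects, smaller subsets and reduced local alpha.

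**What to change.** Optional, and to be settled before unblinding; Section 14.3.14 leaves room for this, since the statistical analysis plan is finalised before the code is broken.

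- In Section 14.3.6.2, for the 11 endpoints, estimate the same marginal difference in response rates by logistic regression on treatment, region, baseline IGA-CHE and the continuous baseline score of that scale. Standardise over the analysis subset, use a robust or delta-method SE, and test one-sided at the local alpha.
- Use the same estimator in the Bernoulli-imputation, tipping-point, pandemic-modified and treatment-policy analyses of these endpoints, so that they differ from the primary analysis only in how data are handled.
- Keep the stratified CMH as a sensitivity analysis.
- Fix an objective trigger for falling back to CMH, such as non-convergence or a stated minimum number of responders per arm. Early visits such as Week 2 are where this could apply.
- Do not simply add baseline bands to the CMH strata. Simulated power changed by only −1 to +3 points with tertiles, and thin strata can cost precision.

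Cost: no new data and one standard model, but the change reaches several paragraphs of Section 14.3.6.2. The binary endpoints would then have two primary methods, and the fallback rule must be written down in advance.

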### First sensitivity analysis for the primary estimand

Missing data at the endpoint of interest, for subjects who do not experience the IEs prior to that, will be handled as follows. For subjects in the delgocitinib cream 20 mg/g group and the cream vehicle group, missing data will be imputed from a Bernoulli distribution with parameter p values 0.1 and 0.2. The same parameter p will be used for both treatment groups. The parameter values 0.1 and 0.2 are based on the response rates of IGA-CHE TS and HESD itch score (weekly average) ≥4 points, respectively, at Week 16 in the cream vehicle group in LP0133-1273 and will introduce uncertainty due to missing data. A MI procedure (100 iterations) will be used for each value of p. For each of the 100 complete datasets, the

Page 111 of 157

difference in response rates will be analysed using a CMH test stratified by region and baseline IGA-CHE score. The results of the analyses will be combined using Rubin's rule to provide the estimated treatment difference and associated standard error, and the 95% CI for the treatment difference will be calculated.

### Second sensitivity analysis for the primary estimand

A tipping point analysis will be performed. Missing data at the endpoint of interest, for subjects who did not experience the IEs prior to that, will be handled as follows:

- For subjects in the delgocitinib cream 20 mg/g group, missing data will be imputed as non-response.
- For subjects in the cream vehicle group, missing data will be imputed from a Bernoulli distribution with parameter p (ranging from 0 to 1). By varying the parameter p, different percentages of subjects in the cream vehicle group will be assumed to be responders, deviating from the default zero percent used in the primary analysis. A MI procedure (100 iterations) will be used for each value of p.

For each of the 100 complete datasets, the difference in response rates will be analysed using a CMH test stratified by region and baseline IGA-CHE score. The results of the analyses will be combined using Rubin's rule to provide the estimated treatment difference and associated standard error, and the 95% CI for the treatment difference will be calculated.

The tipping point is then found as the value of p which changes the conclusion from statistically significant to non-significant and will be judged from a clinical perspective.

### First supplementary estimand: 'pandemic modified composite' strategy

This first supplementary estimand evaluates the treatment effect in adult subjects with moderate to severe CHE, without initiation of rescue treatment or permanent discontinuation of IMP in a world without COVID-19 pandemic, where interest lies in the treatment effect as it would have been observed had the COVID-19 pandemic not happened.

For subjects who experience IEs independent of the pandemic prior to the endpoint of interest, observed data after the IEs will be considered non-response.

For subjects who experience an IE related to the pandemic prior to the endpoint of interest, observed data after the IE will be 'treated as missing' and imputed assuming MAR.

Page 112 of 157

## Primary analysis for the first supplementary estimand

Missing data for subjects who do not attend the visit for the endpoint of interest and do not experience IEs prior to this visit will be imputed as non-response, unless data is missing due to the pandemic in which case it will be imputed assuming MAR.

The procedure for imputing values will be implemented in a 2-step procedure, where all missing or 'treated as missing' data will be imputed using MI (100 iterations) assuming MAR within treatment groups. Once the 100 complete data sets have been generated by MI, non-responder imputation of relevant data points not affected by the pandemic will be applied according to the rules described above.

For each of the 100 complete datasets, the difference in response rates will be analysed using the CMH test stratified by region and baseline IGA-CHE score. The results of the analyses will be combined using Rubin's rule to provide the estimated treatment difference and associated standard error, and the 95% CI for the treatment difference will be calculated.

Second supplementary estimand for endpoints at Week 16: 'treatment policy' strategy This supplementary estimand evaluates the treatment effect in adult subjects with moderate to severe CHE, regardless of initiation of rescue treatment or permanent discontinuation of IMP in a world without COVID-19 pandemic.

Observed data will be used in the analysis, including the data observed after the occurrence of IEs independent of the pandemic. To support the 'treatment policy' strategy, subjects who experience IEs prior to Week 16 will be asked to attend the primary endpoint visit at Week 16 for collection of data.

For subjects who experience an IE related to the pandemic prior to Week 16, observed data at Week 16 will be 'treated as missing' and imputed assuming MAR.

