#### Primary analysis for the second supplementary estimand

Missing data at Week 16 independent of the pandemic will be imputed using MI (100 iterations) assuming MAR within 4 groups defined according to treatment group and whether the subject has experienced an IE (independent of the pandemic).

Missing data or 'treated as missing' data at Week 16 due to the pandemic will be imputed using MI assuming MAR within treatment group using data from subjects who have not experienced an IE.

Page 113 of 157

For each of the 100 imputed datasets, the difference in response rates will be analysed using the CMH test stratified by region and baseline IGA-CHE score. The results of the analyses will be combined using Rubin's rule to provide the estimated treatment difference and associated standard error, and the 95% CI for the treatment difference will be calculated.

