#### Primary analysis for the first supplementary estimand

Missing data for subjects who do not attend the visit for the endpoint of interest and do not experience IEs prior to this visit will be imputed as WOCF (including the baseline value), unless data is missing due to the pandemic in which case it will be imputed assuming MAR.

The procedure for imputing values will be implemented in a 2-step procedure, where all missing or 'treated as missing' data will be imputed using MI (100 iterations) assuming MAR within treatment groups. WOCF imputation of relevant data points not affected by the pandemic will be applied according to the rules described above.

For each of the 100 complete datasets, the change (or percentage change) from baseline to the endpoint of interest will be analysed using the ANCOVA model with effects of treatment,

Page 115 of 157

region, baseline IGA-CHE score, and baseline value. The estimates and standard errors from the analyses will be combined using Rubin's rule to provide the estimate and associated standard error.

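### In the pandemic-modified composite analysis, multiple imputation runs before failures are scored, so outcomes observed after a non-pandemic intercurrent event inform the imputed values

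*Combined protocol and SAP*

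**What the plan says.** Section 14.3.6.2 gives different rules for the two kinds of intercurrent event (IE) under the first supplementary estimand. After an IE independent of the pandemic, "observed data after the IEs will be considered non-response". Only data after a pandemic-related stop of IMP are blanked and then imputed under MAR.

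The primary analysis for that estimand is a two-step procedure. Missing and blanked values are "imputed using MI (100 iterations) assuming MAR within treatment groups". Then: "Once the 100 complete data sets have been generated by MI, non-responder imputation of relevant data points not affected by the pandemic" follows. No limit by IE status is placed on the subjects who inform the imputation.

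Section 14.3.6.3 repeats the two steps for continuous endpoints: "WOCF imputation of relevant data points not affected by the pandemic will be applied according to the rules described above". It does not say that this waits until the imputed data sets exist, so the order is implied rather than stated.

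For the second supplementary estimand, the same kind of pandemic-related value is imputed within treatment group "using data from subjects who have not experienced an IE". That limit appears in both the primary and the sensitivity analysis, for binary and continuous endpoints alike.

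**The concern.** When the imputation runs, a Week 16 value observed after rescue or after a non-pandemic stop is neither missing nor blanked, and its recoding to failure is a later step. On the plain reading it enters as an ordinary outcome. A pandemic-affected subject can then be given a response probability that counts success on rescue as success, while everyone else in the analysis is scored by a rule that counts it as failure.

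Such values will exist. Subjects who stop IMP are asked back at Week 16 (Section 10.3), where Panel 2 schedules IGA-CHE, HECSI and DLQI. HESD entries continue to Week 16 whether or not IMP is stopped (Section 11.3), so HESD endpoints at earlier weeks are exposed too.

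Two groups are little affected. HEIS is not assessed at the primary endpoint visit (Panel 3, footnote 5). For IGA-CHE and HECSI at Weeks 4 and 8, the schedule gives a subject off IMP only the early termination visit before Week 16.

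Nothing planned would reveal the problem. Section 14.3.6.1 promises missing-data sensitivity analyses for the composite and treatment-policy estimands, but none for this one.

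**Working it through.** **The plan's own figure.** Section 14.1 states: "With a one-sided significance level of 2.5%, a sample size of 450 subjects randomised will provide at least 99% power", for 40% against 10%. Splitting 450 in a 2:1 ratio gives 300 and 150.

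- Pooled rate: (300 × 0.40 + 150 × 0.10)/450 = 0.30.
- SE under the null: √[0.30 × 0.70 × (1/300 + 1/150)] = 0.0458.
- SE under the alternative: √(0.40 × 0.60/300 + 0.10 × 0.90/150) = 0.0374.
- z = (0.30 − 1.96 × 0.0458)/0.0374 = 5.62, so power exceeds 99.99%.

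The stated power is reproduced. It does not bear on the imputation, but it supplies anchor rates and a yardstick: the SE of the difference is about 3.7 points.

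**Formulas.** Within an arm, let *c* be the composite response rate, *e* the share with a non-pandemic IE, *r* the response observed after that IE, and *m* the share of subjects whose value is pandemic-affected. Suppose all post-IE values are observed and the imputation depends on arm only.

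- Mean of the values informing the imputation (the pool): *c* + *e r*.
- Target for a subject with a pandemic-related stop, whose non-pandemic IE status is unknown: *c*.
- Target for a subject with no IE who only missed the visit: *c*/(1 − *e*).
- Shift in the difference: *m* × [(pool − target) delgocitinib − (pool − target) vehicle].

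**Inputs.** *c* = 40% and 10% (Section 14.1). The documents give no values for *e*, *r* or *m*. The ranges below are assumptions, with *r* equal in both arms.

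| *e* delgocitinib/vehicle; *r*; *m* | Pool mean | Shift if all had a pandemic-related stop (points) | Shift if all only missed the visit (points) |
|---|---|---|---|
| 5%/10%; 10%; 2% | 40.5%/11.0% | 0.02 × (0.5 − 1.0) = −0.01 | target 42.1%/11.1%: −0.03 |
| 10%/20%; 30%; 5% | 43.0%/16.0% | 0.05 × (3.0 − 6.0) = −0.15 | target 44.4%/12.5%: −0.25 |
| 15%/30%; 50%; 10% | 47.5%/25.0% | 0.10 × (7.5 − 15.0) = −0.75 | target 47.1%/14.3%: −1.03 |

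**Unequal response after the IE (also assumed).** Take IE in 10%/25%, response without IE 44%/13%, response after IE 15%/25%, and *m* = 5%.

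- Composite rates: 0.90 × 44 = 39.6% and 0.75 × 13 = 9.75%.
- Pool means: 39.6 + 0.10 × 15 = 41.1% and 9.75 + 0.25 × 25 = 16.0%.
- Shift for pandemic-related stops: 0.05 × (1.5 − 6.25) = −0.24 points.
- If only half the post-IE values are observed, the pool is (*c* + 0.5 *e r*)/(1 − 0.5 *e*), that is 42.47% and 14.71%. The shift is 0.05 × (2.87 − 4.96) = −0.10 points.

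**Would reversing the order be enough?** Use the same example for subjects with no IE, whose target is 44%/13%. The planned order misses by −2.9 and +3.0 points, or −5.9 in the difference. Setting all failures first misses by −4.4 and −3.25, or −1.15 in the difference. Reversal improves the difference, but it is further from the target in both arms, because it gives these subjects failures they are known not to have had.

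**Simulation.** This used 400 trials of 300/150, 50 imputations, an arm-only imputation and no stratification. For the middle row of the table, the mean difference was 29.9 points with imputation first and 30.1 with failures set first (30.1 with no data missing). For the last row it was 29.5 against 30.2 (30.3 with no data missing). Every run was significant.

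**The case against.** The strongest reply is that contamination is inferred from silence. No imputation model, variable list or input data set is given. The estimand text separately calls post-IE data non-response, and Section 14.3.14 leaves the SAP to be finalised before the code is broken. A programmer could drop these values first. This stands as a limit on certainty. It does not remove the point: for binary endpoints the order is written down, the blanking rule covers only pandemic-related stops, and the donor limit used for the second supplementary estimand is absent.

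The other points largely stand:

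- For continuous endpoints the order is only implied.
- HEIS and the Week 4 and 8 IGA-CHE and HECSI endpoints are largely outside the problem.
- The size rests on assumed rates. Full observation of post-IE values is the less favourable case in the example above, and an imputation model using earlier visits could behave differently.
- The second step does overwrite the outcomes of subjects with a non-pandemic IE, so only the values imputed for pandemic-affected subjects are at issue.
- Simply reversing the two steps would mis-serve subjects with no IE who missed a visit. Panel 23 lists them separately from subjects with a pandemic-related stop.

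**Conclusion.** As written, the imputation rule does not match its own estimand, and it should be corrected. The consequence is small. Under the assumed ranges the shift runs from −0.01 to −0.75 points if every affected subject had a pandemic-related stop, and reaches about −1.0 point at the extreme corner if every one only missed the visit. The planned difference is 30 points, with an SE of about 3.7.

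Three stronger readings are tempting, and the documents support none of them:

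- **The trial's conclusion is at risk.** Section 14.3.5 tests only the primary analysis for the primary estimand, where Panel 23 scores all such data as non-response (WOCF for continuous endpoints).
- **The bias is certainly towards zero.** For pandemic-related stops, that requires *e r* to be larger on vehicle than on delgocitinib. This is plausible, but the documents give neither quantity.
- **Every key secondary endpoint is equally affected.** Exposure is mainly Week 16 IGA-CHE, HECSI and DLQI, plus HESD.

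**What to change.** In Sections 14.3.6.2 and 14.3.6.3, state which data enter the imputation and in what order:

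1. Values observed after a non-pandemic IE do not enter the imputation as observed outcomes.
2. For subjects with no IE whose visit is missing because of the pandemic, impute within arm from subjects without an IE, as the second supplementary analysis already does.
3. For subjects with a pandemic-related stop of IMP, first set outcomes after non-pandemic IEs to non-response (or WOCF), then impute within arm from those composite outcomes.

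Use the same explicit order for binary and continuous endpoints. The cost is SAP wording and program order. No new data are needed, and the change can be made before the code is broken.
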